4. ANALYSIS POPULATIONS

| Population | Definition / Criteria | Analyses Evaluated |
|-----------------------------------|---|---|
| Screened | 
 Comprised of all subjects screened for inclusion in the study. Subjects may be re-screened once, for which they will receive a new subject number. For disposition displays, except for the listing of subjects who were rescreened, only the latest re-screening data will be included. All screening data will be summarized or listed for other displays. | 
 Study Population |
| Randomized | 
 All subjects who were randomly assigned to treatment in the study. In this study, the randomized population includes all enrolled participants, i.e. the randomized population is equivalent to the enrolled population. This population will be based on the treatment the participant was randomized to. | 
 Study Population |
| Safety | 
 All randomized subjects who received at least one dose of study treatment. Participants will be assessed according to actual treatment received. | 
 Safety |
| Intent-to-Treat Exposed (ITT-E) | 
 All randomized subjects who received at least one dose of study treatment. Subjects will be assessed according to their randomized treatment, regardless of the treatment they received. | 
 Study Population Efficacy Health Outcomes |
| Per-Protocol (PP) | 
 All subjects in the ITT-E population with the exception of major protocol violators. Protocol deviations that would exclude participants from the PP population are defined in Section 4.1 (Protocol Deviations) and Appendix 1: Protocol Deviation Management and Definitions for Per Protocol Population). | 
 Efficacy (Sensitivity Analysis) |
| Pharmacokinetic (PK) | 
 All subjects who received CAB and / or RPV and underwent PK sampling during the study and provide at least 1 non-missing CAB and / or RPV plasma concentration value (Non-quantifiable [NQ] values will be considered as non-missing values). | 
 PK |

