| Confirmed Virologic Failure (CVF) | 
 All subjects in the ITT-E population who met Confirmed Virologic Failure (CVF) criteria. | 
 Virology Efficacy |
| Long-term Follow-up (LTFU) | 
 All subjects receiving at least one dose of CAB LA and/or RPV LA who have discontinued the CAB LA + RPV LA regimen and have either at least one Long-term Follow-up phase clinic visit (i.e. have at least one long-term follow-up visit shown in the study database, LTFU month 1, LTFU month 3, etc) or have filled out the LTFU phase conclusion form or have indicated the continuation to LTFU phase in the subject continuation form. | 
 Safety Study Population |

| Population | Definition / Criteria | Analyses Evaluated |
|----------------------------|--|---|
| Week 24 Futility | 
 • All subjects in the ITT-E population who started study treatment at least 168 days prior to the IDMC cut-off date (in order to account for subjects who withdrew early but would have reached Week 24) • The IDMC cut-off date is the predicted Week 24 visit date (Last Subject Last Visit) corresponding to the time at which approximately 50% of subjects have completed Week 24. | 
 • IDMC Futility Analysis (i.e. IDMC Week 24 Analyses) |
| Oral Lead-in | 
 • All subjects who received at least one dose of study treatment during the oral lead-in period in ATLAS-2M study. | 
 • Safety • Study Population • Efficacy |
| Q4W ATLAS | 
 • All subjects in the ITT-E population who were randomized to Q4W arm in ATLAS. | 
 • Health Outcomes |
| SOC | 
 • All subjects in the ITT-E population who either were randomized to SOC arm in ATLAS or did not participate in ATLAS. | 
 • Health Outcomes |
| Oral Bridging | 
 • All subjects in the ITT-E population who received the oral bridging during the Maintenance and/or Extension phases. | 
 • Health Outcomes |

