15.7. Appendix 7: Reporting Standards for Missing Data

15.7.1. Premature Withdrawals

| Element | Reporting Detail |
|---------|---|
| General | 
 Participant study completion (i.e. as specified in the protocol) was defined as 
 Randomly assigned to either treatment group, completed the randomized Maintenance Phase including Week 100 and did not enter the Extension Phase; Randomly assigned to either treatment group, completed the randomized Maintenance Phase including Week 100, and entered and completed the Extension Phase (defined as remaining on study until commercial supplies of CAB LA + RPV LA Q4W or Q8W regimen become locally available or development of CAB LA + RPV LA is terminated). 
Participants who withdraw from CAB LA + RPV LA and go into the LTFU Phase, and participants who withdraw from oral lead-in will be considered to have prematurely withdrawn from the study treatment.
 
In addition to the 52-week Follow-Up phase required for participants who receive one or more injections with CAB LA or RPV LA, an in-clinic Follow-Up visit will be conducted approximately 4 weeks after the last dose of study medication for participants who withdraw during the oral lead-in period with ongoing AEs, and serious adverse events (SAEs) and also any laboratory abnormalities that are considered to be AEs or potentially harmful to the participant, at the last on-study visit. Assessments at the Follow-up visit should reflect any ongoing complaints (e.g., blood draws to follow a laboratory abnormality). Follow-Up visits are not required for successful completion of the study.
 
 Withdrawn participants were not replaced in the study. All available data from participants who were withdrawn from the study will be listed and all available planned data will be included in summary tables and figures, unless otherwise specified. Withdrawal visits will be slotted as per Error! Not a valid result for table.: Assessment Windows or will be summarised as withdrawal visits. |

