15.15.6. List of Data Displays for Week 152 Planned Analyses

15.15.6.1. Study Population Tables

| Study Population Tables | | | | | |
|----------------------------|-------------------------|------------------------|--|---|-------------|
| No. in W152 | Population | IDSL / Example Shell | Title | Programming Notes | Deliverable |
| Subject Disposition | | | | | |
| 1.1 | Randomized | NS1 | Summary of Number of Subjects Enrolled by Country and Site ID | ‘No Treatment’ column is not needed. | W152 |
| 1.2 | Intent-to-Treat Exposed | 207966/primary_15/T1.3 | Summary of Subject Accountability: Study Conclusion Record | Add section for “COVID-19 Relatedness of the Withdrawal” with “Yes”, “No” and “Unknown” categories. | W152 |
| 1.3 | Intent-to-Treat Exposed | 207966/primary_15/T1.4 | Summary of Subject Accountability: Extension Phase Conclusion Record | Add section for “COVID-19 Relatedness of the Withdrawal” with “Yes”, “No” and “Unknown” categories. | W152 |
| 1.4 | Intent-to-Treat Exposed | 207966/primary_15/T1.5 | Summary of Subject Accountability: Maintenance + Extension Phase Conclusion Record | Add section for “COVID-19 Relatedness of the Withdrawal” with “Yes”, “No” and “Unknown” categories. | W152 |
| 1.5 | Long-term Follow-up | 207966/primary_15/T1.6 | Summary of Subject Accountability: Long-term Follow-up Phase Conclusion Record | Add section for “COVID-19 Relatedness of the Withdrawal” with “Yes”, “No” and “Unknown” categories. If there are AEs leading to withdrawal, add sections for outcome and types similarly to 207966/primary_15/T1.5. | W152 |
| 1.6 | Intent-to-Treat Exposed | 207966/primary_15/T1.7 | Summary of Subject Disposition at Each Study Phase | | W152 |

| Study Population Tables | | | | | |
|--|-------------------------|-------------------------|---|---|-------------|
| No. in W152 | Population | IDSL / Example Shell | Title | Programming Notes | Deliverable |
| 1.7 | Intent-to-Treat Exposed | 207966/primary_15/T1.8 | Summary of Reasons for Withdrawal at Each Study Phase | Remove the last footnote in example shell. | W152 |
| 1.8 | Intent-to-Treat Exposed | 207966/primary_15/T1.9 | Summary of Subject Accountability: Withdrawals by Visit (Maintenance + Extension Phase) | | W152 |
| 1.9 | Intent-to-Treat Exposed | 201584/primary_15/T1.10 | Summary of Study Drug Discontinuation | Add section for "COVID-19 Relatedness of the Study Drug Discontinuation" with "Yes", "No" and "Unknown" categories. | W152 |

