15.15.6.4. Safety Tables

| Safety Tables | | | | | |
|-----------------------|------------|------------------------|--|---|-------------|
| No. in W152 | Population | IDSL / Example Shell | Title | Programming Notes | Deliverable |
| Exposure | | | | | |
| 3.1 | Safety | 207966/primary_15/T3.2 | Summary of Extent of Exposure to Study Treatment including SOC Oral Bridging (Maintenance + Extension Phase) | The levels for categorical summaries except for oral lead-in will be selected as appropriate. | W152 |
| 3.2 | Safety | 207966/primary_15/T3.3 | Summary of Needle Length and Gauge for CAB Injection (Maintenance + Extension Phase) | | W152 |
| 3.3 | Safety | 207966/primary_15/T3.4 | Summary of Needle Length and Gauge for RPV Injection (Maintenance + Extension Phase) | | W152 |
| 3.4 | Safety | 207966/primary_15/T3.5 | Summary of Adherence to CAB/RPV Injection Dosing Schedule (Maintenance + Extension Phase) | Replace rows for missed Injection with those specified in Section 15.6.4. Adjust the footnote as appropriate. For missed reloading rows, leave blank for Q4W. | W152 |
| Adverse Events | | | | | |
| 3.5 | Safety | 207966/primary_15/T3.6 | Summary of All Adverse Events by System Organ Class (Maintenance + Extension Phase) | | W152 |
| 3.6 | Safety | 207966/primary_15/T3.8 | Summary of All Adverse Events by System Organ Class and Maximum Toxicity (Maintenance + Extension Phase) | | W152 |
| 3.7 | Safety | 207966/primary_15/T3.8 | Summary of All Adverse Events by System Organ Class and Maximum Toxicity (Extension Phase) | | W152 |
| 3.8 | Safety | 207966/primary_15/T3.9 | Summary of All Adverse Events Excluding Study Drug Injection Site Reactions by System Organ Class and Maximum Toxicity | | W152 |

| Safety Tables | | | | | |
|--|------------|-------------------------|---|-------------------|-------------|
| No. in W152 | Population | IDSL / Example Shell | Title | Programming Notes | Deliverable |
| | | | (Maintenance + Extension Phase) | | |
| 3.9 | Safety | 207966/primary_15/T3.10 | Summary of All On-treatment Adverse Events by System Organ Class and Maximum Toxicity (Maintenance + Extension Phase) | | W152 |
| 3.10 | Safety | 207966/primary_15/T3.11 | Summary of Common Adverse Events (>=5%) by Overall Frequency (Maintenance + Extension Phase) | | W152 |
| 3.11 | Safety | 207966/primary_15/T3.12 | Summary of Common Grade 2-5 Adverse Events (>=1%) by Overall Frequency (Maintenance + Extension Phase) | | W152 |

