| 3.12 | Safety | 207966/primary_15/T3.13 | Summary of All Drug-related Adverse Events by System Organ Class (Maintenance + Extension Phase) | | W152 |
| 3.13 | Safety | 207966/primary_15/T3.15 | Summary of All Drug-related Adverse Events by System Organ Class and Maximum Toxicity (Maintenance + Extension Phase) | | W152 |
| 3.14 | Safety | 207966/primary_15/T3.15 | Summary of All Drug-related Adverse Events by System Organ Class and Maximum Toxicity (Extension Phase) | | W152 |
| 3.15 | Safety | 207966/primary_15/T3.16 | Summary of All Drug-related Adverse Events Excluding Study Drug Injection Site Reactions by System Organ Class and Maximum Toxicity (Maintenance + Extension Phase) | | W152 |
| 3.16 | Safety | 207966/primary_15/T3.17 | Summary of All Drug-Related Grade 2-5 Adverse Events by Overall Frequency (Maintenance + Extension Phase) | | W152 |
| Serious and Other Significant Adverse Events | | | | | |

| Safety Tables | | | | | |
|---------------|---------------------|-------------------------|--|---|-------------|
| No. in W152 | Population | IDSL / Example Shell | Title | Programming Notes | Deliverable |
| 3.17 | Safety | 207966/primary_15/T3.19 | Summary of Serious Adverse Events by System Organ Class (Maintenance + Extension Phase) | | W152 |
| 3.18 | Long-term Follow-up | 207966/primary_15/T3.20 | Summary of Serious Adverse Events by System Organ Class (Long-term Follow-up Phase) | | W152 |
| 3.19 | Safety | 207966/primary_15/T3.22 | Summary of Drug-related Serious Adverse Events by System Organ Class (Maintenance + Extension Phase) | | W152 |
| 3.20 | Safety | 207966/primary_15/T3.23 | Summary of Non-Fatal Serious Adverse Events by Overall Frequency (Maintenance + Extension Phase) | | W152 |
| 3.21 | Safety | 207966/primary_15/T3.24 | Summary of Drug-related Non-Fatal Serious Adverse Events by Overall Frequency (Maintenance + Extension Phase) | | W152 |
| 3.22 | Safety | 207966/primary_15/T3.26 | Summary of Adverse Events Leading to Withdrawal/Permanent Discontinuation of Investigational Product by System Organ Class (Maintenance + Extension Phase) | Adjust the footnote as needed, depending on the given data. | W152 |
| 3.23 | Safety | 207966/primary_15/T3.25 | Summary of Adverse Events Leading to Withdrawal/Permanent Discontinuation of Investigational Product by System Organ Class (Extension Phase) | | W152 |

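### Week 152 adverse event tables limited to the Extension Phase count everyone dosed since Day 1, so their percentages are understated by the share who never entered that phase

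*SAP*

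**What the plan says.** The closing line of Section 4 makes Section 15.15 the place where each display's population is fixed. In the Week 152 list, Section 15.15.6.4, three adverse event tables are restricted to the Extension Phase:

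- Table 3.7: "3.7 | Safety | 207966/primary_15/T3.8 | Summary of All Adverse Events by System Organ Class and Maximum Toxicity (Extension Phase"
- Table 3.14: "Summary of All Drug-related Adverse Events by System Organ Class and Maximum Toxicity (Extension Phase"
- Table 3.23: "Summary of Adverse Events Leading to Withdrawal/Permanent Discontinuation of Investigational Product by System Organ Class (Extension Phase"

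All three list Safety as the population, and all three have empty programming notes. Section 4 defines Safety as "All randomized subjects who received at least one dose of study treatment", with participants assessed by the treatment actually received. It defines no Extension Phase population.

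Section 2.3 describes the Extension Phase as optional. Section 15.7.1 foresees completers who "completed the randomized Maintenance Phase including Week 100 and did not enter the Extension Phase". Table 17 in Section 15.4.1 assigns adverse events to the Extension Phase only for participants who continue into it. For those who go to long-term follow-up instead, events up to the start of follow-up antiretroviral treatment stay in Maintenance.

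An exploratory objective in Section 2.2 is to evaluate safety and tolerability in the participants who are in the Extension Phase. Its endpoints include the incidence of adverse events and the proportion who discontinue because of them.

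**The concern.** Numerator and denominator refer to different groups. The numerator can come only from participants who continued past Week 100, while the denominator is everyone treated from Day 1. Non-entrants are structural zeros, because the phase rules prevent them from ever counting as having an Extension Phase event.

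These three tables are the only adverse event summary tables in the SAP limited to the Extension Phase. A reader who wants to know how often participants in that phase had an adverse event, a drug-related event, or an event leading to discontinuation would take the printed percentages as the answer. They would be too low, and the shortfall is largest in relative terms when many participants left before or at Week 100.

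**Working it through.** The SAP states no Extension Phase count or rate, so there is no figure of its own to reproduce. The check is on the denominator.

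**Inputs**

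- Numerator: participants with an event assigned to the Extension Phase, who are entrants only (Section 15.4.1, Table 17).
- Denominator: Safety, meaning all dosed participants (Section 4, and the Population column in Section 15.15.6.4).
- Share entering the Extension Phase: not in the SAP, so assumed at 80% to 98%.
- Planned size, used for scale only: 510 per arm (Section 1, revision chronology).

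**Formula**

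Reported % = events / N(Safety) = [events / N(entered)] × [N(entered) / N(Safety)] = rate among entrants × share entering.

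Relative understatement = 1 − share entering.

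**Results**

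| Assumed share not entering | 50% among entrants reported as | 2% among entrants reported as |
|---|---|---|
| 2% | 50 × 0.98 = 49.0% | 2 × 0.98 = 1.96% |
| 5% | 50 × 0.95 = 47.5% | 2 × 0.95 = 1.9% |
| 10% | 50 × 0.90 = 45.0% | 2 × 0.90 = 1.8% |
| 20% | 50 × 0.80 = 40.0% | 2 × 0.80 = 1.6% |

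In counts, for the last row: 0.80 × 510 = 408 entrants, of whom 204 have an event. The rate among entrants is 204/408 = 50%, and the printed figure is 204/510 = 40%.

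**Could the table shells restrict the denominator?**

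The shells are not in the document, so this has to be judged from the references to them.

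- Table 3.7 cites the same shell as Table 3.6, and Table 3.14 the same as Table 3.13. Tables 3.6 and 3.13 are Maintenance + Extension tables on Safety.
- Table 3.23 cites a shell whose number matches a Week 96 Maintenance Phase table on Safety (Section 15.15.5.4, Table 3.25).
- Where the SAP wants a special percentage base it writes it into the notes, as in the Week 96 notes to Table 2.37 (Section 15.15.5.2) and Table 3.109 (Section 15.15.5.4).

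Nothing points to a hidden restriction to entrants.

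**The case against.** The strongest points on the other side are these.

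**The denominator is inferred.** It rests on the Population column, the definitions and the empty notes, because the shells are held elsewhere. That caveat stands, but the shared shells and the written exceptions make a silent restriction unlikely.

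**A reader might infer that the comparison of Q8W with Q4W is biased and that the fix would repair it.** If 8% of one arm and 12% of the other did not enter (assumed), equal rates of 50% would print as 50 × 0.92 = 46% and 50 × 0.88 = 44%, a ratio of 0.957. The SAP does not support the conclusion. It gives no entry share by arm. The all-treated denominator also answers a coherent question, namely what proportion of everyone treated had an event starting in the Extension Phase, and it keeps the randomised groups essentially intact. An entrants-only denominator conditions on continuing, which happens after randomisation. If the less tolerant participants leave one arm before Week 100, that arm can look safer among entrants too.

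**A reader might infer that the SAP breaks a stated convention.** It states no such rule. It does use matching populations elsewhere, for example an oral lead-in population ("All subjects who received at least one dose of study treatment during the oral lead-in period in ATLAS-2M study") and the Long-term Follow-up population for Week 152 Table 3.18. Practice is mixed, however: sub-study Table 1.5, on the Return to Gluteal Injection Phase, uses the whole Sub-study ITT-E population (Section 15.15.7.1).

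**A reader might extend the point to disposition Table 1.3,** "Summary of Subject Accountability: Extension Phase Conclusion Record", which lists Intent-to-Treat Exposed (Section 15.15.6.1). That is not an error, because Tables 1.6 and 1.7 in the same list report disposition and withdrawal reasons by phase.

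**The practical effect is limited.** The tables are descriptive, with no test or decision rule attached. That stands.

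**Conclusion.** The point holds for Week 152 Tables 3.7, 3.14 and 3.23. As listed, their percentages do not describe participants in the Extension Phase. They are understated in relative terms by exactly the share of the Safety population that did not enter. The size cannot be computed from the SAP: over an assumed 5% to 20% not entering, 50% becomes 47.5% to 40%, and if nearly everyone entered the effect is small. The conclusion assumes that the Population column sets the percentage base. It does not extend to a claim of a biased contrast between arms, to Table 1.3, or to the combined Maintenance + Extension tables, and no confirmatory result is affected. The change is worth making because it corrects a reported rate at almost no cost.

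**What to change.** For Tables 3.7, 3.14 and 3.23, use as denominator the Safety participants who continued into the Extension Phase, by treatment actually received, and print that number for each arm. This can be done with a new population in Section 4 or with a programming note on each table. Add a footnote that the rates are descriptive and condition on continuing after randomisation, so they are not an unbiased comparison of Q8W with Q4W. Leave the Maintenance + Extension tables on Safety as the comparison between arms. Table 1.3 may be aligned for consistency, but it need not be.

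The cost is one definition or three notes, with no new data. The reported Extension Phase percentages will rise or, if everyone entered, stay the same.

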15.15.6.5. Safety Figures

| Safety Figures | | | | | |
|----------------|------------|-------------------------|--|-------------------|-------------|
| No. in W152 | Population | IDSL / Example Shell | Title | Programming Notes | Deliverable |
| 3.1 | Safety | 207966/primary_15/F3.1 | Plot of Common Adverse Events and Relative Risk - Q8W vs. Q4W (Maintenance + Extension Phase) – Excluding Study Drug ISRs | | W152 |
| 3.2 | Safety | 207966/primary_15/F3.2 | Plot of Common Study Drug Injection Site Reaction Adverse Events and Relative Risk - Q8W vs. Q4W (Maintenance + Extension Phase) | | W152 |
| 3.3 | Safety | 207966/primary_02/F3.6 | Plot of Incidence of Maintenance and Extension Phase Study Drug Injection Site Reaction Adverse Events by Visit (Overall and Common) – CAB and/or RPV | | W152 |
| 3.4 | Safety | 207966/primary_15/F3.7 | Plot of Incidence of Maintenance and Extension Phase Drug-Related Study Drug Injection Site Reaction Adverse Events by Visit (Overall and Common) – CAB | | W152 |
| 3.5 | Safety | 207966/primary_15/F3.8 | Plot of Incidence of Maintenance and Extension Phase Drug-Related Study Drug Injection Site Reaction Adverse Events by Visit (Overall and Common) – RPV | | W152 |
| 3.6 | Safety | 207966/primary_15/F3.21 | Plot of Incidence of Maintenance and Extension Phase Study Drug Injection Site Reaction Adverse Events by Strata and Visit (Overall and Common) - CAB and/or RPV | | W152 |
| 3.7 | Safety | 207966/primary_15/F3.13 | Scatter Plot of Maximum vs. Baseline for ALT (Maintenance + Extension Phase) | | W152 |
| 3.8 | Safety | 207966/primary_15/F3.15 | Scatter Plot of Maximum Total Bilirubin vs. Maximum ALT (Maintenance + Extension Phase) | | W152 |
| 3.9 | Safety | 207966/primary_15/F3.18 | Bar Chart of Lipid NCEP Categories at Week 152 vs. Baseline – Triglycerides, Total Cholesterol, LDL | | W152 |

| Safety Figures | | | | | |
|-----------------------|-------------------|-----------------------------|--|--------------------------|--------------------|
| No. in W152 | Population | IDSL / Example Shell | Title | Programming Notes | Deliverable |
| | | | Cholesterol (Lipids LOCF) | | |
| 3.10 | Safety | 207966/primary_15/F3.19 | Bar Chart of Lipid NCEP Categories at Week 152 vs. Baseline - HDL Cholesterol (Lipids LOCF) | | W152 |
| 3.11 | Safety | 207966/primary_15/F3.20 | Histogram of Timeliness of Injections (Maintenance + Extension Phase) | | W152 |
| 3.12 | Safety | 207966/primary_15/F3.22 | Patient Profile for Subjects with Syncope or Presyncope Adverse Events (Maintenance + Extension Phase) | | W152 |

15.15.6.6. Pharmacokinetic Tables

| Pharmacokinetic Tables | | | | | |
|------------------------|-----------------|------------------------|--|---|-------------|
| No. in W152 | Population | IDSL / Example Shell | Title | Programming Notes | Deliverable |
| 4.1 | Pharmacokinetic | 207966/primary_15/T4.1 | Summary of Plasma CAB PK Concentration (ug/mL) - Time Data by Treatment and Visit (Maintenance + Extension Phase) – Including Log-transformed Statistics | Add Week 156 for Q4W, Week 160 for Q8W. Add following to the second footnote: PK samples were collected at Week 156 (for Q4W subjects) or Week 160 (for Q8W subjects) if Week 152 PK samples were missed (e.g. due to the delays in protocol amendment approvals or site errors). | W152 |
| 4.2 | Pharmacokinetic | 207966/primary_15/T4.2 | Summary of Plasma RPV PK Concentration (ng/mL) - Time Data by Treatment and Visit (Maintenance + Extension Phase) – Including Log-transformed Statistics | Similar notes to above. | W152 |
| 4.3 | Pharmacokinetic | 207966/primary_15/T4.3 | Summary of Evaluable Plasma CAB PK Concentration (ug/mL) -Time Data by Treatment and Visit (Maintenance + Extension Phase) – Including Log-transformed Statistics | Similar notes to above. | W152 |
| 4.4 | Pharmacokinetic | 207966/primary_15/T4.4 | Summary of Evaluable Plasma RPV PK Concentration (ng/mL) -Time Data by Treatment and Visit (Maintenance + Extension Phase) – Including Log-transformed Statistics | Similar notes to above. | W152 |
| 4.5 | Pharmacokinetic | 207966/primary_15/T4.5 | Summary of Evaluable Plasma CAB PK Concentration (ug/mL) -Time Data by Strata and Treatment and Visit (Maintenance + Extension Phase) – Including Log-transformed Statistics | Similar notes to above. | W152 |

| Pharmacokinetic Tables | | | | | |
|------------------------|---------------------|------------------------|--|---|-------------|
| No. in W152 | Population | IDSL / Example Shell | Title | Programming Notes | Deliverable |
| 4.6 | Pharmacokinetic | 207966/primary_15/T4.6 | Summary of Evaluable Plasma RPV PK Concentration (ng/mL) -Time Data by Strata and Treatment and Visit (Maintenance + Extension Phase) – Including Log-transformed Statistics | Similar notes to above. | W152 |
| 4.7 | Long-term Follow-up | 207966/primary_15/T4.1 | Summary of Plasma CAB PK Concentration (ug/mL) - Time Data by Treatment and Visit (Long-term Follow-up Phase) - Including Log-transformed Statistics | Remove the column 'Pl. Time' and the second footnote. | W152 |
| 4.8 | Long-term Follow-up | 207966/primary_15/T4.2 | Summary of Plasma RPV PK Concentration (ng/mL) - Time Data by Treatment and Visit (Long-term Follow-up Phase) - Including Log-transformed Statistics | Remove the column 'Pl. Time' and the second footnote. | W152 |

